11.6 Data management and storage

The Research Assistant will be responsible for collecting the study data. The data will be collected from the Client Health record, Study Log Books (located in the antenatal clinic and postnatal ward) and questionnaires which will be conducted face-to-face and on-line options (using Opinio Survey Software) and over the phone.

The Opinio Survey Software (Opinio 7.1, ObjectPlanet, Inc.) will be the system used to contain, distribute and administer the quantitative survey questionnaire as the on-line option and is available via a free electronic platform through USC. Opinio 7.1 is easily accessible via an email or on-line web link.

The time period for the data collection taken prior to discharge is expected to be over a four to six month period between 06/2017-12/2017. The 6-8 week and 4 month data collection is expected to be from 6/2017-2/2018.

The Midwifery Unit Manager of the Postnatal Ward will be responsible for notifying the research team of adverse events documented in the Client Health Record and PRIME. It is anticipated that this data will be collected between 6/2017-12/2017.

The Midwifery Unit Manager (MUM), Research Fellow, Research Assistant and local Principal Investigator (PI) will have access to the study files in a Qld Health computer, located at the Sunshine Coast University Hospital. All identifiable files will be password protected. This file will contain the list of participants against the allocated study ID.

The Research Assistant will liaise with the Research Team members to upload the collected data into a de-identified Excel Spreadsheet which is also password protected, and located in a separate Queensland Health secure folder. This information will be re-identifiable; a link between Maternal UR and the study code will be kept in a separate and secure password protected file, which will make re-identification of data possible. The re-identifiable data will only be re-identified by the Research Team in exceptional circumstances (i.e. Serious Adverse Event).

The re-identifiable data will be securely stored within Qld Health. De-identified data may be transferred to the University of the Sunshine Coast (USC) for statistical analysis.

Data will remain re-identifiable for the course of the study. Data will then be made non-identifiable for data dissemination processes and storage of final datasets after data collection is complete.

On completion of the study, the data located on files in Qld Health and the USC, as well as data collected in paper form, will be archived in a secure folder and storage company (i.e. GRACE) for no less than fifteen years. Destruction of data will not occur prior to fifteen years after the study has been completed and will be authorised by the Principal Investigator.

11.7 Safety considerations/Patient safety

Midwives will need to attend at least one in-service on the ISSDs prior to setting up and safety briefing associated with the cots. This in-service, will include all aspects associated with the introduction of new hospital equipment as advised by the relevant local hospital committee (EDMS SCACT committee and Infection Management Services), and will inform the clinicians of the manufacturers set up instructions as follows:

- a) MABIM – MaBim Product Brochure.
- b) First Days Pēpi-Pod® - ‘Picture demonstration’ of ‘how to make up and use the Pēpi-Pod, and the ‘Video Clip’ titled ‘Safe, Sleep, Little One’ (CFOC Ltd, 2016).

During Phase 2, monitoring of the newborns by the clinical staff (midwives, doctors) will occur during the usual care of the infant. No additional observations will be made whilst the infant is in the safe sleep device. During the Infant Sleep Observation (ISO), the research assistant / research midwife undertaking the ISO will have a duty of care to notify the clinical midwife caring for the participant, if the mother or baby are found to be sleeping in an unsafe position.

The SSDs are to be cleaned according to the SCHHS cleaning Work Instruction ‘Clean and healthy environments for patients, staff and visitors’ (2016). Clinicians will care for participants in accordance with the SCHHS ‘Safe infant sleeping, co-sleeping and bed sharing guideline’ (2015).

The definition of an **Adverse Event** for the purposes of this study include:

Superficial injury to any part of the body from closing the cot door
Mechanical failure of the MaBim cot.

The definition of a **Serious Adverse Event** for the purposes of this study include:

Neonatal death resulting from suffocation whilst in the SSD
Newborn fall from the SSD to the ground
Newborn treated with antibiotics for a nosocomial infection attributed to SSD use
Newborn admission to the NICU for >72 hours following time spent in the SSD.

The Research Assistant will notify the Principal Investigator of any Adverse or Serious Adverse Event (SAE) immediately to decide causality. The Human Research Ethics Committee and Research Governance Office will be notified of the SAE as soon as possible.

12. SAMPLE SIZE AND DATA ANALYSIS

12.1 Sample size and statistical power

A total of 90 maternal participants and their babies will be recruited (approximately 30 in each group) in this pilot. The primary aim of this pilot is to gather observational data relating to the feasibility and acceptability of the Safe Sleep Enabler options and to test the non-blinded, randomised control trial protocol intended for a larger study.

The Sunshine Coast Hospital and Health Service currently provide services for approximately 2800 birthing women per year. The maternity unit in the Sunshine Coast University Hospital will have approximately 50 maternity beds. Based on an estimated 30-40 eligible births per week, and taking into account conservative participation rates of 40% and attrition post enrolment (50%), in addition to average length of hospital stay (approx. 1-3 days for vaginal deliveries, 3-5 days for delivery by caesarean section), it is anticipated that a maximum recruitment period of 5-6 months will be required to achieve the target sample of 90 eligible mothers and their babies with complete datasets.

The estimated staff population is approximately 80 nurses and midwives; it is anticipated that a target sample size of approximately 65-70 staff (approx. 80% response rate) will be achieved based on previous study participation with this cohort. Power calculations have not been conducted as the population is fixed by the maternity unit setting, and the primary aim of the pilot was to determine feasibility of the protocol and staff acceptance and use of a novel safe sleep enabler in this environment.

Audits of maternal charts and infant sleep observations prior to pilot RCT have been included to provide important baseline relating to current safe sleep practices in this setting. The sample size of 90-100 infant sleep observations and matched maternal chart audits will be adequate to provide a snapshot of current practice; to compare with data collected in previous studies in similar settings (Young et al., 2010); is feasible to collect within a relatively short period of time using in-kind time and resources available to the investigating research team; and provides the SCUH with valuable data to meet state guideline recommendations relating to current monitoring of safe sleep practices (Queensland Health, 2013).

Sample size calculations for the larger study have been conducted. Current exclusive breastfeeding rates in Australia are estimated at approximately 38% at infant age 3 months. An improvement of 5-10% associated with an intervention would be considered clinically significant given the health outcomes afforded by breastfeeding. Breastfeeding rates at 3 months were used to determine sample size. With a 90% power at an alpha level of 0.05, anticipating a small to moderate effect of $\delta=0.1$, it was determined that we will require $n=454$ in each group. A total of 1,362 postnatal mothers and their babies will be recruited in the larger RCT. To allow for 50% attrition, due to ineligibility after delivery, 2,040 families will be approached which is determined to be achievable within a 12-14 month recruitment period at this site.

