9. STUDY POPULATION

The study population will comprise of a) eligible women who birth at the Sunshine Coast University Hospital during the period of recruitment (estimated June – November 2017) and their babies, and b) nursing staff who provide care to mothers and their babies in the postnatal setting (inclusive of registered midwives, registered nurses and enrolled nurses).

Sunshine Coast Hospital and Health Service currently provides services for approximately 2800 birthing women per year. The Maternity Unit in the Sunshine Coast University Hospital will have approximately 50 maternity beds. Using calculations based on eligible births per week, conservative participation rates, attrition post enrolment, in addition to average length of hospital stay, it is anticipated that a target sample of 90 eligible mothers and their babies with complete datasets will be achieved in 4- 6 months.

The total population of staff members for the study sample is approximately 80 nurses and midwives; it is anticipated that a target sample size of approximately 65-70 staff will participate based on previous study participation with this cohort.

All patients and staff members who meet inclusion criteria will be approached to participate. Specific inclusion and exclusion criteria will be applied.

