If the allocated cot is not available (i.e. the First Days Pepi-Pod® or MaBim are already in use) the participant will be allocated to a standard cot. These allocations will be managed as a fourth group in the analysis in which demographic information should theoretically be similar to the standard cot allocated group. This method also serves as an internal checking procedure for the randomisation process used in the clinical environment. In this instance, the midwife in charge will make an entry in the Project Register for participant name, envelope number, first cot allocation, non-availability and reallocation to standard cot and will place the envelope into the discard box (to allow checking of integrity of the randomisation process).

A total of 300 envelopes will be prepared representing each of the three options equally (100/100/100) and which will also allow for the envelope discard process. A mock run of the randomisation process indicated that based on an estimated 7 deliveries per day and an average stay of 3 days, the four MaBim cots would be in almost constant use and approximately half of those mother-baby pairs randomised to the MaBim would be allocated

to use them. This process will allow integrity of the randomisation of process while still maintaining recruitment for each target sample within a feasible timeframe.

An allocation to a cot is intended for the duration of hospitalisation. The usual length of hospital stay for a woman having a vaginal delivery is 1-3 days; for a woman delivering by caesarean section 3-5 days. Analyses will be by Intention to Treat according to actual allocation and Actual Use, consistent with a recent randomised controlled study of safe sleep enabler use (Baddock et al., 2017).

The study will continue until there is a minimum of 60 participants in each group (total n=180) and will allow an attrition rate of up to 50% during the 4 month follow-up period following discharge from the post-natal unit. The final target sample for this pilot is 30 participants in each group with a complete data set.

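### Section 12.1 gives 90 as the number of mothers recruited, whereas section 11.3, section 9 and 12.1's own next paragraph make 90 the number with complete data, which needs 180 enrolled at 50% attrition

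*Protocol*

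**What the plan says.** The size of the maternal sample appears in four parts of the protocol.

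- **Section 12.1, first sentence:** "A total of 90 maternal participants and their babies will be recruited (approximately 30 in each group) in this pilot". Here 90 is the intake.
- **Section 12.1, second paragraph:** the recruitment period is worked out from "conservative participation rates of 40% and attrition post enrolment (50" per cent), in order "to achieve the target sample of 90 eligible mothers and their babies with complete datasets". Here 90 is the number left after attrition.
- **Section 9:** "a target sample of 90 eligible mothers and their babies with complete datasets will be achieved in 4- 6 months". Again 90 is the number with complete data.
- **Section 11.3:** "The study will continue until there is a minimum of 60 participants in each group (total n=180"), and the study "will allow an attrition rate of up to 50% during the 4 month follow-up period". It then says "The final target sample for this pilot is 30 participants in each group with a complete data set". Here 180 is the intake and 90 (3 x 30) the yield.

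The budget in section 16 costs consent for 90, and its labour totals are also built on 90 participants.

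Table 1 in section 11.4 places the maternal acceptability questionnaire before discharge. Feeding method, breastfeeding self-efficacy, attachment and safe-sleep practice are followed to 4 months.

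**The concern.** The same figure cannot be both the number recruited and the number with complete data when the plan allows for losing up to half. Section 12.1 is where a reader looks for the sample size, and its first sentence gives half the enrolment that section 11.3 requires.

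If staff worked to 90, the 4-month data meant to inform the larger trial would fall well short of the stated target, and the primary maternal outcome would be estimated on half the intended number. Feasibility is also a primary outcome, and recruitment cannot be judged cleanly against two targets that differ two-fold. If staff worked to 180, the budget would cover the participant-level tasks for only 90.

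**Working it through.** **Inputs.** Complete-data target: 30 per group, 90 in all (11.3; the total also in 9 and 12.1). Attrition: up to 50% (11.3), 50% (12.1). Three options in equal numbers (11.3: "A total of 300 envelopes will be prepared representing each of the three options equally (100/100/100")). Eligible births 30-40 per week and participation 40% (12.1). Labour per participant: 160 minutes and $156.45 (16).

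**1. Reproduce the plan's figure.** Enrolment = target / (1 - attrition).
- Per group: 30 / (1 - 0.5) = 60.
- Total: 90 / (1 - 0.5) = 180.

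Both match section 11.3, which is internally consistent.

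**2. Complete datasets per group.** Recruited x (1 - attrition) / 3.

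| Attrition | 90 recruited | 180 recruited |
|---|---|---|
| 0% | 30 | 60 |
| 10% | 27 | 54 |
| 20% | 24 | 48 |
| 30% | 21 | 42 |
| 40% | 18 | 36 |
| 50% | 15 | 30 |

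With 90 recruited, the target of 30 is met only if nobody is lost.

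**3. Precision for acceptability.** It is measured before discharge, so the denominators are about 90 / 3 = 30 or 180 / 3 = 60 per group. Section 9.7 cites 86% of mothers recommending one of the devices in another trial; I use a nearby proportion only as an illustration. Exact (Clopper-Pearson) 95% intervals:
- 26/30 (87%): 69% to 96%.
- 52/60 (87%): 75% to 94%.

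**4. Does 180 fit the recruitment window?** Enrolment per week is 30 x 0.4 = 12 to 40 x 0.4 = 16.
- 180 enrolled: 180 / 16 = 11.25 to 180 / 12 = 15 weeks.
- 90 enrolled: 90 / 16 = 5.6 to 90 / 12 = 7.5 weeks.

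On these rates 180 fits within the 4-6 months stated, and 90 would need far less than that.

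**5. Budget.** The stated totals reproduce at 90 participants: 90 x 160 / 60 = 240 h; 90 x $156.45 = $14,080.50; chart recall $360 / $4 = 90 charts. At 180:
- Every task done for everyone: 180 x 160 / 60 = 480 h; 180 x $156.45 = $28,161.
- Half (90) do not complete follow-up questionnaires 2 and 3 (30 min, $29.33): 480 - 45 = 435 h; $28,161 - 90 x $29.33 = $25,521.30.

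**6. Meaning of a group.** Section 11.3 expects about half of those randomised to MaBim to receive a standard cot because no device is free, and treats reallocated mothers as a fourth group in the analysis. If 60 are randomised to MaBim, about 60 x 0.5 = 30 would use it. If the 60 must be users, about 60 / 0.5 = 120 MaBim allocations are needed, more than the 100 envelopes prepared. The one-half comes from a mock run at 7 deliveries per day (49 per week), well above 12-16 enrolments per week, so the real share may be lower; the definition still has to be stated.

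**The case against.** The best defence is that this is one loosely worded sentence. The only explicit rule for continuing enrolment is in 11.3, at 180. Three other statements, one of them in the next paragraph of 12.1, define 90 as complete datasets, and the recruitment window suits 180 better than 90. All of that stands, and it makes a wording error the likeliest explanation. It does not make the sentence correct, and the budget shows that 90 participants was also used as a working figure elsewhere.

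Four stronger readings are tempting and are not supported.

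- A reader might infer that acceptability would rest on 15 per group, with an interval such as 60% to 98% for 13/15. Table 1 collects acceptability before discharge, so 4-month attrition does not reduce it; the comparison is about 30 against 60.
- A reader might take 15 per group as the expected yield. Section 11.3 says up to 50%, so 15 is the planning limit. The 50% in 12.1 runs from enrolment, which follows consent around 36 weeks of gestation and precedes randomisation on the ward, so it may not be the same quantity as the follow-up attrition in 11.3.
- A reader might infer two competing stopping rules, or two different trials. Section 12.1 states a number but no rule for stopping.
- A reader might infer that labour cost must double to $28,161. That is an upper bound, because it charges follow-up questionnaires to mothers who are lost. Whether a shortfall would harm follow-up cannot be shown from the protocol.

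**Conclusion.** The point holds. The first sentence of 12.1 contradicts section 11.3, section 9 and its own next paragraph by a factor of two. Taken literally, it gives about 15 complete datasets per group at the 50% limit, and fewer than 30 under any attrition at all. It also halves the number available for acceptability, widening an illustrative interval from 75%-94% to 69%-96%, which is a modest loss.

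These figures assume equal thirds across the three options and attrition spread evenly between them. The intervals assume acceptability near 87%, which is not a figure the plan sets for this trial.

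The severity is moderate. The pilot is descriptive, has no power calculation for its own maternal sample, and states the workable enrolment rule in 11.3. The correction is needed because the sample size statement itself is wrong, and because the budget and the undefined meaning of a group have to be settled along with it.

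**What to change.** 1. **Section 12.1, first sentence.** Replace with: *A minimum of 180 mothers (60 per group) will be enrolled, to give at least 30 per group (90 in total) with complete 4-month data, allowing for up to 50% attrition.*
2. **Acceptability.** Add that this outcome, collected before discharge, is analysed on all participants with data, both as randomised and by actual cot use, in line with 11.3 and 12.2.
3. **Section 11.3.** State whether the minimum of 60 counts mothers by the cot randomised or the cot received. If it is the cot received, more than 180 may have to be randomised and the envelope supply needs checking.
4. **Section 16.** Reconcile the budget with 180 participants: at most 480 h and $28,161 of labour, or about 435 h and $25,500 if half do not complete the follow-up questionnaires. If only 90 can be funded, restate the complete-data target in 11.3, section 9 and 12.1 as about 15 per group at 50% attrition.

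Items 1 to 3 are changes of wording. If a group means the cot randomised, no participants are added beyond what 11.3 already requires. Item 4 needs a re-costing and either more funding or a lower stated target.

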12.2 Data analysis

Data collection and analyses will include maternal and infant demographics; breastfeeding outcomes (at discharge, 6-8 weeks and 4 months); length of stay; maternal-infant attachment; maternal satisfaction and perceptions relating to enabler use; staff time to recruit and educate families, perceptions relating to intervention impact and adverse events; and maternal and

staff awareness of safe sleep recommendations (self reported and observed). Data from this pilot, the first Australian trial of a hospital postnatal safe sleep enabler, will be used to inform a randomised controlled trial of safe sleep enablers in postnatal environments.

Maternal Data: Analysis of maternal data will be conducted using the principles of intention to treat. All participants who were enrolled and randomly allocated to treatment are included in the analysis and will be analysed in the groups to which they were randomised. A further analysis will be based on actual use, consistent with a recent published study on Wahakura use, a Maori safe sleep enabler, intended for domestic use after discharge home to the community (Baddock et al., 2017) which performed analyses based on intention to treat and actual use.

Statistical analyses will be performed to report the prevalence and proportions of variables surveyed. Questionnaire results will be entered into a purpose-built Microsoft Excel database for data cleaning and preparation for statistical analysis. A 10% random selection (approximately 9-10 questionnaires from each of the maternal records, staff survey and audits) will be double entered to assess data-entry accuracy and intra-rater reliability. Consistency checks will be performed on all variables to ensure that only valid responses will form the basis of the ensuing analysis.

Quantitative data will be analysed using descriptive techniques such as frequency and percentage and measures of central tendency and distribution (for example, mean and standard deviation or median and IQR). Normality of data will be assessed. Group comparisons to comparing equivalency of control and interventions will be conducted with Chi-squared test for categorical measures and analysis of variance or Kruskal-Wallis test for continuous measures as appropriate assessing for normality and equality of variances.

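### Larger-RCT planning figures: approaching 2,040 families does not cover the stated 50% attrition (2,724 would), and the 12-14 month recruitment period conflicts with the protocol's own 40% participation rate

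*Protocol*

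**What the plan says.** Section 12.1 of the Protocol closes with a calculation for the larger trial that the pilot is meant to prepare. The control rate is given as follows: "Current exclusive breastfeeding rates in Australia are estimated at approximately 38% at infant age 3 months". The effect is delta = 0.1, and the error rates are stated as "With a 90% power at an alpha level of 0.05". The result is 454 in each of three groups, or 1,362 mothers. Neither sidedness nor the test is given, nor whether 454 refers to a pairwise or an overall three-arm comparison.

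The allowance for loss is then: "To allow for 50% attrition, due to ineligibility after delivery, 2,040 families will be approached". On timing, the sentence ends with the claim that this is feasible locally: "which is determined to be achievable within a 12-14 month recruitment period at this site".

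Earlier in section 12.1, the pilot's recruitment is worked out from 30-40 eligible births per week, "taking into account conservative participation rates of 40% and attrition post enrolment (50" per cent). Section 11.3 describes the pilot's 50% differently, saying that the study "will allow an attrition rate of up to 50% during the 4 month follow-up period".

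Section 4.1 makes the feasibility of a large randomised trial under this protocol the third primary objective.

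**The concern.** Two statements in the planning paragraph do not follow from the figures beside them. The number to approach appears to come from multiplying by 1.5 where a 50% loss requires dividing by 0.5. The recruitment period appears to leave out the participation rate that the same section applies to the pilot.

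The stake is the plan for the next trial. A reader who takes 2,040 families and 12-14 months at face value would expect a single-site RCT to be comfortably feasible at 90% power. On the protocol's own rates it would under-recruit in that time, and if half of those entered were lost it would fall below the stated power. Nothing in the pilot's own data collection or analysis depends on these numbers.

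**Working it through.** **Inputs, all from Protocol section 12.1.** Control rate 38%; delta 0.1, read as an absolute difference (38% v 48%); alpha 0.05; power 90%; 454 per group; total 1,362; attrition 50%; 2,040 approached; 12-14 months; 30-40 eligible births per week; 40% participation (given for the pilot); about 2,800 births per year in the health service.

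**1. Number to approach.**
- Total: 3 x 454 = 1,362. Reproduced.
- n x (1 + d): 1,362 x 1.5 = 2,043. This matches 2,040 apart from rounding.
- n/(1 - d): 1,362/0.5 = 2,724. This is the number that leaves 1,362 after a 50% loss.
- Loss that 2,040 can absorb: 1 - 1,362/2,040 = 33%.
- Left after a 50% loss from 2,040: 1,020, or 340 per arm.

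**2. Power with 340 per arm.** The pairwise power is Phi[(d x sqrt(n) - z x sqrt(2p(1-p))) / sqrt(p1(1-p1) + p2(1-p2))], with p1 = 0.38, p2 = 0.48, p = 0.43 and d = 0.1. The three-arm figure uses a non-central chi-square on 2 df with non-centrality n x sum((pi - mean)^2) / (mean x (1 - mean)). The protocol names no test for this calculation, so several are shown.

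| Test at alpha 0.05 | Power, 340 per arm | Power, 454 per arm |
|---|---|---|
| Two-sided pairwise, 38 v 48% | 75% | 86% |
| One-sided pairwise, 38 v 48% | 84% | 92% |
| Three-arm chi-square, 38/38/48 | 79% | 89.6% |
| Three-arm chi-square, 38/48/48 | 78% | 89.0% |
| Three-arm chi-square, 38/43/48 | 65% | 78% |

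No row reaches 90% with 340 per arm. With 454 per arm the answer depends on the test. For a two-sided pairwise test, 90% power needs 513 per arm, so 454 does not reproduce under that test. For the overall test with 38/38/48, 461 per arm is needed, which is close to 454.

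**3. Recruitment time.** Weeks per month are taken as 52/12.
- Enrolled per week at 40% participation: 30 x 0.4 = 12 to 40 x 0.4 = 16.
- Enrolled in 12 months at the lower rate: 12 x 52 = 624. Enrolled in 14 months at the higher rate: 16 x 14 x 52/12 = 971. The requirement is 1,362.
- Time to enrol 1,362 with no loss at all: 1,362/16 = 85 weeks to 1,362/12 = 114 weeks. The stated period is 52 to 61 weeks.
- Obtaining 1,362 from 2,040 approached implies a yield of 1,362/2,040 = 67%. At 40% the yield would be 2,040 x 0.4 = 816.
- Cross-check on all births: 2,800 x 14/12 x 0.4 = 1,307, still below 1,362 before eligibility is considered.

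**The case against.** The strongest reply concerns the word approached. Approaching 2,040 families in 12-14 months is possible: the period yields about 1,560-2,427 eligible births, and 14 months suffices from about 34 per week. The 40% is a figure for the pilot, it is called conservative, and the protocol does not assign it to the RCT. This much stands: the recruitment sentence is not impossible in itself. But if 2,040 counts families approached, it must absorb both refusal and later loss, and 1,362 from 2,040 leaves room for neither 40% participation nor 50% attrition. If a higher participation rate is expected in the RCT, it has to be stated.

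It is also fair to say that these are provisional figures. Sections 5.1 and 10.1 define feasibility through staff support, consent, randomisation, safety briefing and documentation. The protocol nowhere sets 2,040 or 12-14 months as a criterion for the pilot to meet. That limits the weight of the point without making the arithmetic right.

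Four stronger readings are tempting, and the document does not support them.
- *454 per arm does not give 90% power.* That holds for a two-sided pairwise test, but section 12.1 states no test or sidedness. One-sided gives 92%, and an overall chi-square, the test section 12.2 names for the pilot's group comparisons, gives about 89-90% under two of the patterns above. The paragraph also mentions gains of 5-10%, but it says that delta = 0.1 was used, so the powered end of that range is visible.
- *The RCT faces two successive 50% losses.* Section 11.3's figure concerns the pilot's follow-up. No text says that the RCT expects it on top of ineligibility after delivery.
- *Only 136 per arm would remain* (2,040 x 0.4 x 0.5 = 408). This carries both pilot rates into the RCT, a scenario that the protocol never states.
- *The pilot cannot check the 38% because of its schedule.* The text says "Breastfeeding rates at 3 months were used to determine sample size", whereas the pilot collects "breastfeeding outcomes (at discharge, 6-8 weeks and 4 months"). These times bracket 3 months, and with about 30 complete controls no single time point could verify 38% usefully. The mismatch is immaterial here.

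**Conclusion.** The point holds for two planning figures. First, 2,040 is wrong for the stated 50% attrition: 2,724 is needed to retain 1,362, and 2,040 covers a 33% loss. This rests only on the protocol's own 1,362 and 50%. The consequence, 340 per arm with power of 75% to 84% pairwise and 78-79% for the overall test with 38/48/48 or 38/38/48, assumes that all 2,040 enter and half are then lost. Second, 12-14 months at this site conflicts with 30-40 eligible births per week at 40% participation, which enrols about 624-971 against 1,362. This assumes that the pilot's participation rate carries over to the RCT, for which no other rate is given.

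Two matters need only clarification: what the 50% covers, and which test lies behind 454.

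A reader might infer that the pilot itself is undersized or its analysis compromised. It is not: its target of 90 complete datasets and its analysis do not use these numbers. The severity is moderate. The figures bear on primary objective 3 as planning assumptions, and the error is cheap to correct.

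**What to change.** In Protocol section 12.1:

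1. Replace 2,040 by 2,724 for 454 per arm, or keep 2,040 and state that it allows for 33% loss.
2. Reconcile the recruitment period with 40% participation (about 85-114 weeks for 1,362 before any loss), or state the higher participation rate assumed for the RCT. Say whether 2,040, or its replacement, counts families approached or mothers enrolled.
3. Say whether the 50% covers ineligibility after delivery only, or also loss to follow-up.
4. State the test and sidedness behind 454, and restate n or power to match. If the intended test is two-sided pairwise, either give the power at 454 as 86% or use 513 per arm for 90%. The latter makes 3 x 513 = 1,539 in total and 1,539/0.5 = 3,078 with 50% attrition.

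The cost is recalculation and wording in one paragraph, with no extra pilot participants. The downside is that the stated feasibility of the RCT at this site becomes less favourable.

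### The larger trial's allowance for 50% attrition multiplies by 1.5 instead of dividing by 0.5, so 2,040 families cover only a 33% loss

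*Protocol*

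**What the plan says.** The last paragraph of Protocol section 12.1 sizes the larger randomised trial, not the pilot. Its inputs are a control rate ("Current exclusive breastfeeding rates in Australia are estimated at approximately 38% at infant age 3 months"), an effect ("anticipating a small to moderate effect of $\delta=0.1") and error rates ("With a 90% power at an alpha level of 0.05"). The result is: "it was determined that we will require $n=454$ in each group". The total follows: "A total of 1,362 postnatal mothers and their babies will be recruited in the larger RCT". The allowance for losses comes next: "To allow for 50% attrition, due to ineligibility after delivery, 2,040 families will be approached". The same sentence calls this number achievable at the site in 12–14 months.

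Two other places bear on the check. Section 11.3 applies a 50% allowance to the pilot: the enrolled number is given as "total n=180) and will allow an attrition rate of up to 50% during the 4 month follow-up period", with 30 per group to be left with complete data out of 60. Earlier in section 12.1, the pilot's recruitment forecast assumes 30–40 eligible births per week and 40% participation, in addition to 50% attrition after enrolment.

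**The concern.** The required total, the loss rate and the inflated number stand in consecutive sentences and do not agree. Half of 2,040 is well short of 1,362. The pattern is a common slip: a loss rate is added to the required number, when the required number should be divided by the proportion retained. At 10% the two differ little; at 50% they differ by a third.

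The pilot does not use 2,040, but the number still matters. Section 4.1 makes the feasibility of a large trial under this protocol a primary objective, and section 12.2 says that the pilot data will inform that trial. If feasibility is judged against 2,040 families in 12–14 months, the target would deliver three quarters of the sample that the protocol says it needs.

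**Working it through.** **Inputs.** From section 12.1: 454 per group, 1,362 in total, 50% loss, 2,040 families, control rate 38%, effect 0.1, alpha 0.05, 30–40 eligible births per week, 40% participation. Three equal groups are taken from section 11.3, where the pilot's envelopes are prepared "representing each of the three options equally (100/100/100"); this agrees with 3 × 454 = 1,362.

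**1. Reproducing the plan's figure.** Required number × (1 + loss): 1,362 × 1.5 = 2,043. Per group, 454 × 1.5 = 681; rounding to 680 gives 3 × 680 = 2,040. The stated figure is reproduced this way. Division by the proportion retained does not reproduce it.

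**2. What 2,040 leaves at 50% loss.** 2,040 × (1 − 0.5) = 1,020; 1,020 / 3 = 340 per group. The shortfall is 1,362 − 1,020 = 342 mothers, or 25% of the requirement.

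**3. What loss 2,040 can absorb.** 1 − 1,362 / 2,040 = 0.332, about 33%.

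**4. What 50% loss requires.** 1,362 / (1 − 0.5) = 2,724, or 908 per group, which is 684 more than 2,040. The pilot's figures in section 11.3 follow this form: 90 / 0.5 = 180.

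**5. Power, if entry stopped at 2,040.** Assumptions that the Protocol does not spell out: 0.1 is a 10-point absolute rise (38% to 48%), the test is two-sided, and groups are compared in pairs without adjustment. With mean rate 0.43:

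power = Φ{[0.10·√n − 1.96·√(2 × 0.43 × 0.57)] / √(0.38 × 0.62 + 0.48 × 0.52)}

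- n = 454: (2.131 − 1.372) / 0.697 = 1.09, power about 86%.
- n = 340: (1.844 − 1.372) / 0.697 = 0.68, power about 75%.

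The attrition slip therefore costs about 11 points. Under the same assumptions, 90% power needs 513 per group, so 454 falls short of 90% before any losses.

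**6. Recruitment time.** This assumes that the 30–40 eligible births per week also apply to the larger trial and that every eligible woman is approached and agrees.

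| Families | At 40 per week | At 30 per week |
|---|---|---|
| 2,040 | 51 weeks (about 12 months) | 68 weeks (about 16 months) |
| 2,724 | 68 weeks (about 16 months) | 91 weeks (about 21 months) |

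Fourteen months is about 61 weeks, and 61 × 40 = 2,440. So 2,724 does not fit in the stated window even at the top of the range.

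**7. Before or after consent.** If the count is of families approached and 40% agree, as assumed for the pilot, then 2,724 / 0.4 = 6,810 would have to be approached.

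**The case against.** **This is a future study.** Section 6 describes the present work as an observational pilot that supports the design of a later trial, and section 4.1 expects its results to lead to protocol revisions. No enrolment target, analysis or safety rule of the pilot uses 2,040. This stands, and it limits the severity.

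**2,040 may be only a screening forecast.** The loss is attributed to ineligibility after delivery. In the pilot, consent is sought at the 36-week visit (section 11.1) and randomisation takes place on arrival in the postnatal unit (section 11.3), so many such losses would come before randomisation. A low forecast could then mean longer recruitment and not a smaller analysed sample; the pilot itself continues until a minimum per group is reached. This also stands. A reader might infer that the larger trial would end with 340 per group. The text does not say that entry stops at 2,040, so that outcome is conditional.

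**50% may loosely mean half as many again.** The pilot's 50% concerns loss during follow-up, not ineligibility after delivery, so it does not prove what was meant here. But the plain sense of 50% attrition is that half are lost, and the only worked use of such a rate in the document (180 to 90) has that sense. Nothing in section 12.1 defines it otherwise.

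**The power loss.** A reader might set 75% against the stated 90% and charge all 15 points to the attrition slip. The figures do not support this: 454 per group gives about 86% under the same assumptions, and the remaining 4 points belong to the derivation of 454.

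**Conclusion.** The sentence is wrong on its own figures. A number that allows for 50% attrition from a requirement of 1,362 is 2,724; the stated 2,040 allows for 33%, and at 50% it leaves 1,020, or 340 per group. This uses only 1,362, 50% and 2,040, and holds whatever the basis of 454.

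Two consequences rest on assumptions. The fall in power from about 86% to about 75% requires that entry stops at 2,040 and that the target is 38% versus 48%, two-sided and pairwise. The 16–21 months for 2,724 families requires the pilot's 30–40 eligible births per week with no refusals; refusals would lengthen it.

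The error concerns the planning of the larger trial. A reader might infer that the pilot is undersized too, but its 60 enrolled per group for 30 complete is correct at 50% loss. The point is a worthwhile correction to the feasibility target, not a must-fix for the pilot.

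**What to change.** Correct the last paragraph of section 12.1 in one of two ways.

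1. **Keep the 50% loss.** State that 2,724 consenting families are needed before the loss. Say whether the number of families approached is counted before or after consent; with 40% participation about 6,810 would have to be approached. Revise the 12–14 month claim in the same sentence. Replacing 2,040 by 2,724 alone would leave that claim in conflict with the site's own birth figures.
2. **Keep 2,040.** State that it allows for 33% attrition, or that 50% attrition leaves 340 per group, with about 75% power for 38% versus 48% (two-sided 0.05, pairwise).

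Either way, the cost is a few sentences of planning text, and nothing changes in the pilot's enrolment, conduct or analysis. The first option makes the recruitment outlook visibly less favourable, which is information that a feasibility study should give. The derivation of 454 should be checked separately, because any change to it carries through to all of these totals.
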